8 STUDY ASSESSMENTS AND PROCEDURES

A participant will be considered lost to follow-up if they fail to return for two scheduled visits and is unable to be contacted by the study site staff.

The following actions must be taken if a participant fails to return to the clinic for a required study visit:

- The site will attempt to contact the participant and reschedule the missed visit within 24 hours and counsel the participant on the importance of maintaining the assigned visit schedule and ascertain if the participant wishes to and/or should continue in the study.
- Before a participant is deemed lost to follow-up, the Principal Investigator or designee will make every effort to regain contact with the participant (where possible, 3 telephone calls and, if necessary, a certified letter to the participant's last known mailing address or local equivalent methods). These contact attempts should be documented in the participant's medical record or study file.
- Should the participant continue to be unreachable, they will be considered to have withdrawn from the study with a primary reason of lost to follow-up.

7.3 LOST TO FOLLOW-UP

We will assess feasibility of the study (primary outcome) and potential effectiveness (secondary outcome - visual acuity, reading speed, visual fields and quality of life) of IVR stimulation. A feasibility assessment is required as such home-based visual rehabilitation approach using IVR HMD for children has never been tested.

8.1 ASSESSMENTS

Feasibility will be assessed in real-time every 2 days during and after home-based IVR stimulation. The device, the Oculus Quest 2 will record feasibility outcome measures, sent the data to a dedicated and secured laboratory computer through Wi-Fi. The number of completed trials, blocks and sessions will be compared to the protocol.

Visual assessments performed at every study visit will include:

- Best Corrected Visual Acuity, distance and near vision (ETDRS chart, Colenbrander chart).
- Mean fixation stability (MAIA micro-perimeter).
- Contrast sensitivity (FACT test).
- Points not seen – Humphrey full field 120 (HFA3, Zeiss)
- Points not seen – Esterman binocular field (HFA3, Zeiss)
- Mean Reading speed (wpm – Minnesota Low Vision Reading test, MNREAD test²⁸).
- Quality of life scores (Children's Vision Function Questionnaire²⁹).

8.2 ADVERSE EVENTS AND SERIOUS ADVERSE EVENTS

Safety will be assessed by adverse events (AEs), premature withdrawals for AEs, rates of AEs.

8.2.2 DEFINITION OF SERIOUS ADVERSE EVENTS (SAE)

An Adverse Event (AE) is any untoward medical occurrence associated with the use of an intervention in a study participant, which does not necessarily have a causal relationship with the intervention. An AE can therefore be any unfavourable and unintended sign (including an abnormal laboratory finding), symptom or disease temporally associated with the use of the intervention, whether or not considered related to the investigational intervention.

Stable chronic conditions which are present prior to entry in the study and do not worsen are not considered AE. These pre-existing conditions will be documented in the participant's medical history.

AEs will be the primary safety endpoints. Known AEs induced by IVR stimulation are nausea, dizziness and disorientation. The severity of these AEs will be scored using the validated VRISE questionnaire. A VRISE score < 25 is considered as an AE. Three (3) consecutive VRISE scores < 25 will lead to the withdrawal of the study.

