Primary outcome corresponds to the feasibility of the study in terms of adherence, retention rates and recruitment. We specified, a priori, 4 feasibility objectives for our pilot study to be considered successful:

1. $\geq 8/10$ patient (80%) completed the protocol.
2. IVR stimulation protocol is considered complete if the patient performed ≥ 12 sessions out of 15.
3. ≤ 3 consecutive VRISE score < 25 per patient during the treatment period.
4. ≤ 2 dropouts (20%) for cybersickness (discomfort symptoms experienced in VR)

Completion of the sessions will be monitored in real-time. After each block, a data sheet (.csv, 2 kb) containing device ID#, subject #, date/time, time to complete the task/block, number of tasks/blocks performed, total stimulation time, total duration of the session will be sent though Wi-Fi to a dedicated and secured laboratory computer in real-time (if no Wi-Fi access is available at the end of each block, data are stored in the device and sent as soon as Wi-Fi is again available – data storage capacity 500 Mo. No extra costs are incurred to the patients' Wi-Fi plan for sending data). Each session contains 3 data sheets. A session is considered complete when 3 blocks of 5 min stimulation are performed. If no data sheets are received on the lab's computer for a period of 3 consecutive days or missed/incomplete sessions are observed, the participant's parent will be contacted by phone and email to identify the cause (no Wi-Fi, Oculus Go malfunction, dropout) and appropriate action will be taken. Before and after each session, the participant will answer to the VRISE questionnaire (5 questions scored 1 to 7 using the Oculus Go). After the completion of the questionnaire, the detailed score will be sent though Wi-Fi to a dedicated and secured laboratory computer in real-time.

Secondary outcome corresponds to potential effectiveness of IVR stimulation measured by visual perception and quality of life assessed following standard procedures used in low-vision rehabilitation²⁷ and collected at the low-vision clinic by ophthalmologists. Endpoints will measure change from baseline at 2 and 4 weeks in:

- Best Corrected Visual Acuity, distance and near vision (ETDRS chart, Colenbrander chart).
- Mean fixation stability (MAIA micro-perimeter).
- Contrast sensitivity (FACT test).
- Points not seen – Humphrey full field 120 (HFA3, Zeiss)
- Points not seen – Esterman binocular field (HFA3, Zeiss)

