9.4.4 SAFETY ANALYSES

We will report results using descriptive statistics (including frequency distributions, a measure of central tendency and a measure of dispersion) average VRISE scores.

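### Read as a sum of five 1-7 items, the VRISE adverse event trigger cannot detect one item at its worst level alone, and 9.4.4 plans no item-level summary that would show it

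*Combined protocol and SAP*

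**What the plan says.** Section 4.1 says that before and after each session "the participant will answer to the VRISE questionnaire (5 questions scored 1 to 7 using the Oculus Go"). It adds that "the detailed score will be sent though Wi-Fi to a dedicated and secured laboratory computer in real-time". The five items are not listed, the aggregation is not stated, and nothing says which end of the scale means no symptom.

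The adverse event definition (printed under heading 8.2.2) first gives a general definition that covers any unfavourable symptom, whether or not related to the intervention. It then states "AEs will be the primary safety endpoints" and "Known AEs induced by IVR stimulation are nausea, dizziness and disorientation", says that VRISE scores the severity of these events, and adds the trigger: "A VRISE score < 25 is considered as an AE". It ends with "Three (3) consecutive VRISE scores < 25 will lead to the withdrawal of the study".

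Section 8.2.4 lists three ways of eliciting adverse events: volunteered reports from participants or parents, three consecutive VRISE scores below 25, and observation by investigators or staff. All adverse events must be documented.

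Section 9.4.4 plans descriptive statistics, including frequency distributions, "a measure of central tendency and a measure of dispersion) average VRISE scores". No item-level summary is planned. Feasibility criterion 3 (sections 4.1, 9.1 and 9.4) uses the same cutoff on the same score.

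**The concern.** The protocol names three distinct symptoms as known adverse events, but its only automatic trigger is a cutoff on one overall score. A total over five items lets four unaffected items offset one that is badly affected. If the offset is large enough, a child can enter the worst possible response on an item after a session without the rule reacting.

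Tolerability at home is one of the main things this ten-patient pilot is meant to establish. If isolated severe symptoms pass the trigger and are then absorbed into summaries of overall scores, both the safety summary and feasibility criterion 3 could look better than the children's experience. The child would already have entered the information on the device; the plan does not say that anyone looks at it by item.

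**Working it through.** The plan gives no derivation for the cutoff of 25, so there is no figure to reproduce. The check is to see which response patterns the rule can register.

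**Inputs**

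| Input | Value | Source |
|---|---|---|
| Items and range | 5 items, each 1 to 7 | 4.1 |
| Trigger | score below 25 | 8.2, adverse event definition |
| Aggregation | not stated; sum inferred | see step 1 |
| Direction | not stated; low = worse inferred | see step 1 |
| Item content | not stated | – |

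**Step 1: scoring.** A mean, or a single item, cannot exceed 7, so every response would fall below 25. The score must be a sum, with range 5 × 1 = 5 to 5 × 7 = 35. If high meant worse, a symptom-free child would total 5 and count as an adverse event. So low is worse and 7 means no symptom.

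**Step 2: points needed.** The highest total that triggers is 24, so a child must lose at least 35 − 24 = 11 points. One item can lose at most 7 − 1 = 6. Since 6 < 11, one item alone can never trigger the rule.

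**Step 3: cases**

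| Pattern (remaining items at 7) | Total | Below 25? |
|---|---|---|
| one item at 1 | 1 + 4 × 7 = 29 | no |
| two items at 2 | 2 + 2 + 3 × 7 = 25 | no |
| one at 1, one at 3 | 1 + 3 + 21 = 25 | no |
| one at 1, one at 2 | 1 + 2 + 21 = 24 | yes |
| two items at 1 | 1 + 1 + 21 = 23 | yes |
| three items at 3 | 9 + 2 × 7 = 23 | yes |

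With one item at 1, the rule reacts only if the other four sum to 23 or less, that is, lose at least 28 − 23 = 5 further points.

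**Step 4: all patterns.** Of the 7^5 = 16,807 possible response patterns:

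- exactly one item below 7: 0 of 30 trigger (lowest total 29);
- exactly two items below 7: 30 of 360 trigger;
- exactly three items below 7: 1,080 of 2,160 trigger.

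These are counts of patterns, not probabilities; the documents give no symptom rates.

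**Step 5: consequence for one child.** A child with one item at 1 and the rest at 7 after each of 15 sessions produces 0 of 15 post-session scores below 25, and these scores do not count against feasibility criterion 3.

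**Step 6: the two adverse event passages side by side.** In the definition, one score below 25 is an adverse event. In 8.2.4, the VRISE route to an adverse event is three consecutive scores below 25. A child with one or two isolated low scores has adverse events under the first and is not picked up by the VRISE route of the second. This conflict does not depend on how the score is formed.

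**The case against.** The strongest objection is that the safety endpoint is adverse events, not VRISE-defined adverse events. The general definition already covers any unfavourable symptom, and nothing says that a score of 25 or more rules one out. Section 8.2.4 adds volunteered reports and observation. Missed or incomplete sessions prompt contact with the parent (4.1), clinic visits fall at weeks 2 and 4, and feasibility criterion 4 counts dropouts for cybersickness whatever the VRISE total. All of this stands. A reader might infer that a child with one severe symptom is never recorded and that the safety endpoint is bound to be undercounted. The documents do not support that: undercounting is a risk, not a certainty.

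A second tempting inference is that no single named symptom can trigger the rule. That would require each symptom to map to one item, and the items are not listed. A symptom that lowers two items to 1 gives 23 and does trigger.

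Third, 9.4.4 includes frequency distributions, so reporting is not confined to a mean. That is correct, but the quantity summarised is still the average VRISE score and not the items.

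Fourth, the rule does react to moderate discomfort spread over several items, and the questionnaire is described as validated. Whether 25 is an established cutoff cannot be judged from the documents, and it is not challenged here.

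These safeguards do not close the gap. Staff observation is largely unavailable during home sessions, contact with parents follows missed or incomplete sessions or absent data rather than an item response, and no section says item responses are reviewed.

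**Conclusion.** The point holds as a limitation of the trigger and of the planned summary. On the inferred scoring (sum, low = worse), the VRISE rule cannot detect one item at its worst with the others unaffected (29) or two items at the second-worst level (25). Such a symptom remains an adverse event by definition, but its capture in home sessions rests mainly on someone volunteering it, and 9.4.4 would not show it. The tolerability conclusion could therefore be too favourable. The size cannot be calculated, because the documents give neither symptom rates nor item content.

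Separately, and without any scoring assumption, the one-score rule in the definition and the three-consecutive-score route in 8.2.4 disagree and must be reconciled. For a ten-patient pilot with descriptive safety reporting, this is an inexpensive improvement in safety detection and not a fault that invalidates the design.

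**What to change.** Keep the total-score rule. Then:

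1. In 9.4.4, add an item-level table built from the detailed scores already sent after each questionnaire. For each item, give the distribution of post-session scores and of the change from before to after the session, the number of children and of sessions with worsening, and each child's worst item score. Using the change keeps a stable pre-existing symptom from being read as an effect of the session, in line with the protocol's exclusion of stable chronic conditions from adverse events.
2. State in 8.2 that item-level worsening is reviewed against the general adverse event definition.
3. State how the VRISE score is formed, which end is worse, and what the five items cover.
4. Reconcile the adverse event definition (one score below 25) with 8.2.4 (three consecutive scores below 25).

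No new adverse event cutoff or stopping rule is proposed; those are for the sponsor. The cost is one extra table, a few sentences of text, and possibly a higher reported adverse event count. No new data collection is needed.

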8.2.1 DEFINITION OF ADVERSE EVENTS (AE)

AE are classified as serious or non-serious. A Serious Adverse Event is any AE that is:

- fatal
- life-threatening
- requires or prolongs inpatient hospital stay
- results in persistent or significant disability or incapacity
- a congenital anomaly or birth defect
- an important medical event

The term "life-threatening" in the definition of "serious" refers to an AE in which the participant was at risk of death at the time of the event. It does not refer to an AE that hypothetically might have caused death if it were more severe.

Serious Adverse Events will be documented for any incident that:

- (a) is related to a failure of the device or a deterioration in its effectiveness, or any inadequacy in its labeling or in its directions for use; and
- (b) has led to the death or a serious deterioration in the state of health of a patient, user or other person, or could do so were it to recur. "Serious deterioration in the state of health" means: a life-threatening disease, disorder or abnormal physical state; the permanent impairment of a body function or permanent damage to a body structure; or a condition that necessitates an unexpected medical or surgical intervention to prevent such a disease, disorder or abnormal physical state or permanent impairment or damage.

8.2.3 CLASSIFICATION OF AN ADVERSE EVENT

VRISE questionnaire for assessing AEs related to audiovisual IVR stimulation will be recorded electronically (.csv file) after each home-based session (every 2 days) and sent through Wi-Fi to a dedicated and secured laboratory computer in real-time.

8.2.3.1 SEVERITY OF EVENT

The severity of an AE is assessed by VRISE questionnaire:

- Three (3) consecutive VRISE scores < 25 will lead to the withdrawal of the study.

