7 DISCONTINUATION AND WITHDRAWAL

Discontinuation from visual training does not mean discontinuation from the study, and remaining study procedures should be completed as indicated by the study protocol. If a clinically significant finding is identified (including, but not limited to changes from baseline) after enrollment, the PI or qualified designee will determine if any change in participant management is needed. Any new clinically relevant finding will be reported as an Adverse Event (AE).

Withdrawn patient will go for a final visit at the clinic with primary and secondary outcome assessment. Primary outcomes (adherence, VRISE scores, retention) collected until the withdrawal date will be analyzed. Secondary outcomes (BCVA, fixation stability, contrast sensitivity, reading speed, visual fields and quality of life) will be assessed during final visit and analyzed.

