7.2 PARTICIPANT DISCONTINUATION/WITHDRAWAL FROM THE STUDY

Participants are free to withdraw from participation in the study at any time upon request.

An Investigator may discontinue or withdraw a participant from the study for the following reasons:

- Withdrawal of informed consent (participant or parent/guardian withdraw for any reason)
- If any clinical Adverse Event (AE), laboratory abnormality, or other medical condition or situation occurs such that continued participation in the study would not be in the best interest of the participant
- Significant study intervention non-compliance
- Disease progression which requires discontinuation of the study intervention
- Requirement of prohibited concomitant medication(s) that requires discontinuation of the study intervention
- Three consecutive VRISE scores < 25 during the 4-week home-based audiovisual IVR stimulation procedure will terminate the investigational intervention.

The reason for participant discontinuation or withdrawal from the study will be recorded in the study "Study termination" CRF. Participants who sign the informed consent form and are randomized but do not receive the study intervention may be replaced. Participants who sign the informed consent form, and are randomized and receive the study intervention, and subsequently withdraw, or are withdrawn or discontinued from the study, will be replaced. The data from participants who are withdrawn or discontinued from the study will be used in the analysis unless the participant requests otherwise.

The Oculus Quest 2 device will be turned off remotely preventing its use by the participant. The participant will return the Oculus Go/Quest including all the equipment (storage box, batteries, remote control, straps) at the final visit.

Withdrawn patients will be replaced to reach a total number of 10 evaluable patients.

Patients will be contacted after 24 hours by phone or email and evaluated for residual virtual-reality symptoms and effects (VRISE questionnaire).

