9 STATISTICAL CONSIDERATIONS

9.1 STATISTICAL HYPOTHESES

- Primary Endpoint(s):

Feasibility is considered when the following primary endpoints criteria are met:

1. $\geq 8/10$ patient (80%) completed the protocol.
2. IVR stimulation protocol is considered complete if the patient performed ≥ 12 sessions out of 15.
3. ≤ 3 consecutive VRISE score < 25 per patient during the treatment period.
4. ≤ 2 dropouts (20%) for cybersickness (discomfort symptoms experienced in VR)

- Secondary Endpoint(s):

Secondary endpoint measures will be performed at Toronto Western hospital during baseline (visit 1), after 2 weeks (visit 2), after treatment at 4 weeks (visit 3) and at 1-month (visit 4) and 6 months (visit 5) follow-up. Results will be compared to baseline.

Visual acuity:

- Best Corrected Visual Acuity (BCVA) scores for distance and near vision – ETDRS/Colenbrander charts.
- Fixation stability - MAIA microperimeter, CentreVue
- Contrast sensitivity – FACT test.

Field of Vision:

- Humphrey full field 120 – Humphrey Field Analyzer 3, Zeiss
- Esterman binocular field - Humphrey Field Analyzer 3, Zeiss

Reading Speed:

- Minnesota Low Vision Reading - MNREAD test.

Quality of life:

- Children's Vision Function Questionnaire (39 questions)

- Exploratory Endpoint(s):

None

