9.4 STATISTICAL ANALYSES

9.4.1 GENERAL APPROACH

Results will be reported using descriptive statistics (mean, 95%CI).

Normality of the distribution will be assessed (skewness and kurtosis). If not normally distributed, data will be transformed (Log_{10}) or non-parametric Kruskal-Wallis test will be used.

Bayesian repeated measures ANOVA will be used to analyze and compare baseline, 2 weeks, 4 weeks, 1 month and 6 months outcome measures.

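### The VRISE stopping rule takes a child out of the study in 8.2 and 8.2.3.1 but, by the wording of sections 7 and 7.2, stops only the training; the 1-month and 6-month results may then leave out children who did not tolerate IVR

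*Combined protocol and SAP*

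**What the plan says.** **The trigger.** Section 8.2.3.1 reads "Three (3) consecutive VRISE scores < 25 will lead to the withdrawal of the study". The adverse-event definition in section 8.2 carries the same sentence.

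**The same trigger in section 7.2.** There, three low scores in a row during home training "will terminate the investigational intervention". That bullet stands in a list of reasons for which an investigator may take a participant out of the study.

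**Stopping training.** Section 7 states: "Discontinuation from visual training does not mean discontinuation from the study, and remaining study procedures should be completed as indicated by the study protocol".

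**Leaving the study.** Section 7 provides one assessment: "Withdrawn patient will go for a final visit at the clinic with primary and secondary outcome assessment". Section 7.2 adds: "Withdrawn patients will be replaced to reach a total number of 10 evaluable patients". Data from withdrawn participants are kept unless they ask otherwise.

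**Use of the late data.** Section 9.1 lists secondary measurements at visits 1 to 5 and says "Results will be compared to baseline". Section 9.4.1 says "Bayesian repeated measures ANOVA will be used to analyze and compare baseline, 2 weeks, 4 weeks, 1 month and 6 months outcome measures". Section 9.3 defines the intention-to-treat set as everyone registered. Section 9.4 gives no method for missing values.

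**The concern.** One event has two stated consequences, and the documents do not say which governs. The choice decides whether a child who tolerates VR poorly is seen again at 1 and 6 months.

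If such children leave the study, those who remain at days 58 and 200 have been selected by tolerability. The late change from baseline would then describe children who could use the headset, although the analysis set is meant to include everyone registered. In a pilot that also looks at potential effectiveness in ten children, one or two such losses form a visible share of the data. Staff also need a single instruction before the first case arises.

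**Working it through.** The plan gives no figure to reproduce, so the check is mainly a comparison of texts.

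**Step 1: the two readings.**

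| | 8.2 and 8.2.3.1 | Section 7 and the words of the 7.2 bullet |
|---|---|---|
| Three scores in a row below 25 | Child leaves the study | IVR sessions stop |
| Assessments afterwards | One final visit | Remaining visits in section 1.3 |
| Days 58 and 200 | None provided (inference) | Attended |

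**Step 2: which visits are at stake.** Section 1.3 has post-baseline visits on days 14, 28, 58 and 200, with Humphrey and Esterman fields on days 28, 58 and 200. Under the 8.2 reading, days 58 and 200 have no provision. Whether days 14 and 28 are also missed depends on two things:

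- *When the rule triggers.* Sections 3 and 4.1 collect VRISE before and after each session. If both scores count, three in a row are possible by the second session (day 3). Section 8.2.3 mentions only scores after the session; on that basis the earliest trigger is the third session (day 5). Both precede day 14.
- *When the final visit is held.* Section 4.1 uses that term for the 4-week visit (visit 3), but section 7 sets no date for a withdrawn child.

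No fixed count of lost visits therefore follows from the text.

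**Step 3: how many children.** No stop rate is given. Criterion 4 in section 9.1 accepts at most 2 cybersickness dropouts. If both were VRISE stops and 8.2 were followed, the late data would lack 2 of 10 children (20%), or 2 of 12 (17%) after replacement. Replacement restores the number observed; it does not bring back the missing children. With no stops, none are lost.

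**Step 4: is the direction of bias known?** Let N be the number registered, k the number stopped, and c the stopped children's mean gain divided by the others' mean gain, taken as positive. The mean of those observed, relative to the mean of all registered, differs by N / ((N − k) + c·k) − 1. The values of k and c are assumptions; N is 10, or 10 + k with replacement.

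| k | N | c = 0 | c = 0.5 | c = 1 | c = 1.5 |
|---|---|---|---|---|---|
| 1 | 10 | +11.1% | +5.3% | 0 | −4.8% |
| 2 | 10 | +25.0% | +11.1% | 0 | −9.1% |
| 1 | 11 | +10.0% | +4.8% | 0 | −4.3% |
| 2 | 12 | +20.0% | +9.1% | 0 | −7.7% |

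For example, k = 2, N = 10 and c = 0 give 10 / 8 − 1 = 25.0%; with c = 1.5 they give 10 / (8 + 3) − 1 = −9.1%. The sign depends on whether c is below or above 1, and the documents say nothing about c.

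**Step 5: what is unaffected.** Section 7 keeps the primary data up to withdrawal and analyses the secondary outcomes from the final visit. The four feasibility criteria concern sessions completed, VRISE runs during treatment and cybersickness dropouts. None uses a day 58 or day 200 measurement.

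**The case against.** **The texts can be reconciled.** The 7.2 bullet is in a list of study-withdrawal reasons, and that section goes on to remote switch-off, device return and replacement. On this view 7.2, 8.2 and 8.2.3.1 all mean study withdrawal, and the specific VRISE rule overrides the general statement in section 7. This is a possible reading. It departs from the bullet's own words, however, and it makes the loss of late follow-up consistent without removing it.

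**The loss is inferred.** No sentence says that a withdrawn child skips visits 4 and 5. This stands. The inference rests on the plan providing only a final visit and then a replacement.

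**Triggers may be rare.** Section 5.2 excludes children with three low scores in a row at inclusion and those with a history of vertigo or dizziness. Section 2.3 expects less discomfort in children than in adults. This stands too, and the number may be zero.

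**Little depends on it.** This is a single-arm pilot with uncontrolled before-after comparisons, and section 6.3 says that nothing is done to limit bias. That lowers the weight of the point. It is no reason to keep a rule that discards follow-up the protocol has already scheduled.

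**Stronger readings.** A reader might infer that the late results are inflated by 10% to 25%. Those figures need 1 or 2 stops and no gain at all in the stopped children, neither of which is in the documents. A reader might also infer that exactly 2 of the 4 post-baseline visits are lost; the timing of the trigger and of the final visit leaves that open. Nor do the documents support the idea that the feasibility verdict turns on the missing late data.

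**Conclusion.** The conflict is real: the same event is given two consequences, and the version in 8.2 and 8.2.3.1 serves the late comparisons worse. Followed literally, it gives the child one final visit. By inference, there is no 1-month or 6-month assessment, and depending on timing the day 14 or day 28 visit may also be missed as scheduled. The day 58 and day 200 secondary results would then omit children who did not tolerate IVR, although the intention-to-treat set includes them.

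The direction and size of any bias cannot be determined from the documents. The effect is zero if no child triggers the rule, or if stopped children change as much as the others. The point deserves correction because section 7 already contains the better principle. It does not undermine the feasibility assessment.

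**What to change.** 1. Reword 8.2 and 8.2.3.1 so that three VRISE scores in a row below 25 permanently stop IVR sessions only. Move the 7.2 bullet to section 7.1, on discontinuing the intervention.
2. Keep the remote switch-off of the headset and the 24-hour VRISE check for these children.
3. State that the child is asked to attend the remaining visits in section 1.3, through days 58 and 200, unless consent is withdrawn.
4. State that the child stays in the intention-to-treat set, still counts as a cybersickness dropout under criterion 4, and is a non-completer if fewer than 12 sessions were done. This has to be explicit: a child who stays in follow-up might otherwise not be called a dropout, and a run of exactly three low scores triggers the stop yet still meets criterion 3, which allows up to three.

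The stopping threshold does not change. Replacement policy and any revised completion threshold are separate matters and not part of this change.

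**Cost.** No visit or test is added to the schedule. A family that has stopped training is asked to attend up to 4 visits of 1.5 hours (4 × 1.5 = 6 hours) in place of one final visit. The change needs a protocol amendment; the text on protocol deviations in section 10.1 requires sponsor agreement and documented research ethics board approval.
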